2.4 Framework

All endpoints are tested for superiority of the intervention programme over control.

2.5 Statistical Interim Analyses and Stopping Guidance

As no relevant adverse events are unlikely, no stopping guidelines are planned.

2.6 Timing of the Final Analysis

The final analysis will take place when all outcomes have been collected and the database is locked.

2.7 Timing of Outcome Assessments

Data will be obtained at different time points over a period of at least 12 months and at most 36 months (on average 24 months). The trial will end when 109 relapses have been documented or after 125 PwMS have reached 24 months of follow-up. The measurement time points are calculated based on the randomization date. t_1 takes place before enrolment and t_0 before randomization, t_1 to t_{12} are scheduled every three months. Deviations from the ideal time point are allowed to the degree of ± 21 days. For all participants, who have not reached t_{12} , the final telephone interview t_x takes place after the final participant reaches t_8 . Table 2 displays the assessment of variables within these time points.

Table 2 Assessments and measurement time points**Instrument**

	Screenin	Baseline	Allocatio	Post allocation												tx
				t ₁	t ₂	t ₃	t ₄	t ₅	t ₆	t ₇	t ₈	t ₉	t ₁₀	t ₁₁	t ₁₂	
Month	t ₋₁	t ₀		3	6	9	12	15	18	21	24	27	30	33	36	X
Eligibility screen	X															
Informed consent	X															
Sociodemographic data	X	X														
Randomization			X													
Relapse history				X	X	X	X	X	X	X	X	X	X	X	X	X
Relapse questions				(X)	(X)	(X)	(X)	(X)	(X)	(X)	(X)	(X)	(X)	(X)	(X)	(X)
Decision autonomy and satisfaction				(X)	(X)	(X)	(X)	(X)	(X)	(X)	(X)	(X)	(X)	(X)	(X)	(X)
CPS relapse				X												
PAM and empowerment scale		X		X				X				X		X	X	X
HAQUMS	X							X								
HADS	X							X								
PBMS relapses			X					X								
UNDS	X							X	X	X	X	X	X	X	X	X
Relapse risk knowledge				X				X								
Physician visit including EDSS	X							X								
EQ-5D-5L	X		X				X				X		X	X	X	X
Health economic parameters	X		X	X	X	X	X	X	X	X	X	X	X	X	X	X

(x): in case of relapse

3 Statistical Principles

3.1 Confidence intervals and p-values

All tests will be performed two-sided on a significance level of 5%. Confidence intervals (CI) will be reported with 95% confidence level.

3.2 Adherence and protocol deviations

In order to ensure patient adherence, the usage of the IG and CG programme is monitored. Participants will be contacted by phone every three months.

3.3 Analysis populations

Primary analysis is planned following the intention-to-treat principle. The intention-to-treat population contains all randomised patients. For the primary endpoint, only definite and possible relapses are considered.

4 Trial population

4.1 Screening data

Screening data will be reported and described within a CONSORT flowchart.

4.2 Eligibility

Persons aged between 18 and 65 years with suspected or diagnosed relapsing-remitting MS with ≥ 1 relapse in the last year and/or ≥ 2 relapses in the last 2 years will be included. Only PwMS having access to the internet, being fluent in German and providing signed informed consent will be included.

PwMS being allergic to steroids as well as PwMS with primary or secondary progressive MS, an acute relapse, severe cognitive deficit, severe visual impairment or severe psychiatric disorder will be excluded. Participation in the parallel study POWER@MS1 or in the former training programme on relapses will lead to exclusion.

4.3 Recruitment

Recruitment numbers will be reported and described within a CONSORT flow diagram.

4.4 Withdrawal/follow-up

Participants may leave the study at any time and may withdraw consent. Reasons for study withdrawal will be documented using a CONSORT flowchart.

4.5 Baseline patient characteristics

All baseline patient characteristics will be summarized using descriptive statistics (e.g. mean, standard deviation, median, IQR for continuous variables and frequencies (percentages) for categorical variables) and appropriate graphical methods (e.g. boxplots, histograms, barplots) depending on the data type.

5 Analysis

5.1 Outcome definitions

A full list of outcomes and their timing is described in Section 2.7.

Ten adapted items of the **Patient Activation Measure (PAM13)** are used to assess empowerment (Zill, 2013). The items of the PAM13 range from 1 (Disagree at all) to 4 (Fully agree). The raw score is the sum of the items divided by the number of answered questions (excepting non-applicable items) and multiplied with 10. Afterwards the raw score is transformed to a range from 0 to 100 (Moljord, 2015).

$$\text{10-item PAM calculation expressed as formula: } 100 \times \frac{\left(\frac{\text{sum score}}{\text{Number of answered questions}} \times 10 \right) - 10}{(40-10)}.$$

An adapted empowerment scale with three of the five items from Bann *et al* (2010) was used to assess empowerment. The items are answered on the 3-point scale: "no," "yes, a little," or "yes, a lot."

Control Preference Scale (CPS) is used to assess preferred and realised role preference in steroid treatment decision-making. It consists of five roles ranging from A (the individual making the treatment decisions), over C (the individual making the decisions jointly with the physician) to E (the physician making the decisions). Satisfaction with the decision will be measured in a telephone interview within 3 months in case a decision for or against steroid treatment has been made.

Hamburg Quality of Life in MS Scale Version 10.0 (HAQUAMS) is a questionnaire for measuring quality of life in PwMS (Gold *et al.*, 2001). It consists of 44 items with mostly 5-point-likert scale. Twenty-eight of the items are subdivided into the six subscales:

- Fatigue: Items 6, 7, 8, 9
- Cognition: Items 10, 11, 12, 13
- Lower extremity: Items 17, 18, 19, 20
- Upper extremity: Items 21, 22, 23, 24, 25
- Communication: Items 29, 30, 31, 32, 33, 34
- Mood: Items 36, 37, 38, 39, 40.

Mean subscale scores are calculated, the total score is built by calculating the mean of the subscale score means: *HAQUAMS total score = mean(mean(upper extremity), mean(lower extremity), mean(fatigue), mean(cognition), mean(communication), mean(mood))*. Subscale and total score range from one to five; high scores indicate low quality of life. For missing items, mean substitution is allowed.

Planned Behaviour in MS Scale (PBMS relapses) is adapted to steroid decision-making and is used to measure behaviour strategies in case of relapses (Kasper, 2012). The 18-item questionnaire consists of six sub-domains. Items are measured on a four-step Likert-scale format ranging from “strongly disagree” (0) to “strongly agree” (3). Eight items are negatively framed and their polarity is reversed (Items: 5, 8, 9, 10, 13, 16, 17, 18). Three items each are allocated into the six sub-domains as follows:

- 1a) Expectations regarding the effects of immunotherapy: Items 1, 7, 13
- 1b) Importance of the expected effects: Items 4, 10, 16
- 2a) Assumptions regarding the expectations of relevant social partners: Items 2, 8, 14
- 2b) Importance of the social norm: Items 5, 11, 17
- 3a) Assumptions regarding the control belief: Items 3, 9, 15
- 3b) Importance of the control belief: Items 6, 12, 18

Scale means are calculated for the sub-domains, whereby missing values are interpolated if necessary. The three main domain scores are obtained by the multiplication of the corresponding two sub-domains, e.g. 1a) x 1b). The total score is the mean of the three products. A higher score indicates a more critical attitude on short-term high-dose corticosteroids during relapses.

Expanded Disability Status Scale (EDSS) is determined by the treating neurologist in order to assess impairment (Kurtzke, 1983). It ranges from 0 to 10, with higher scores indicating greater disability.

United Kingdom Neurological Disability Scale (UNDS) will be used to assess impairment (Heesen, 2007). It consists of the 12 domains *cognitive disorders, mood, vision, communication, swallowing, upper extremity, lower extremity, bladder, intestine, fatigue, sexuality and pain* with sub-scores ranging from 0 to 5. The score, the sum of the 12 sub-scores, ranges from 0 to 60, with higher scores indicating greater disability. If the *sexuality score* is unknown, it can be imputed by the mean of *lower limb, bladder* and *intestine score* rounded to the nearest integer.

Hospital Anxiety and Depression Scale (HADS) is a self-reported questionnaire and is used as a measure for depression and anxiety (Zigmond, 1983). It consists of two 7-item subscales, one for anxiety and one for depression, with a maximum score of 21 for each subscale (each item is scoring from 0 to 3), with higher scores representing higher levels of anxiety or depression. A maximum of one missing item per subscale can be estimated by the rounded mean of the six existing items of the same subscale.

Relapse risk knowledge is used to assess risk knowledge and has been adapted to reflect current evidence (Köpke, 2009). The questionnaire consists of nine multiple-choice questions and one free-response question. The score is obtained by the number of correct answers and ranges from 0 to 10, with higher scores indicating better knowledge.

Hamburg Relapse Assessment Scale (HARAS) is used to assess relapses in more detail (Köpke, 2011). 24 items of the questionnaire are used and each item is scored on a 5-point Likert scale, with higher scores indicating greater risk of relapse. The total score is calculated by summing the item scores.

5.2 Analysis methods

In the analysis of primary and secondary endpoints, centres with less than 10 patients are pooled into one centre.

The primary endpoint is analysed using a generalised linear model with mixed effects and logit link function. Subject-specific effects are modelled as random effects, while intervention group and study centre are included as fixed effects. In case of nonconvergence due to a flat likelihood in the variance of the subject-specific effects near 0, the model will be simplified by removing the random subject-specific effects resulting in a generalized linear model (logistic regression). In this case correction of standard errors by using generalized estimating equations (GEE) will be explored. The intervention effect is reported as odds ratio (OR) with 95% CI and p-value testing the null hypothesis of no intervention effect ($H_0: OR = 1$).

```
library(MASS)

prim.mod <- glmer(oral_treated ~ intervention + site + (1|Patient.Id),
                  data = primEnd, family = binomial(link = "logit"))
summary(prim.mod)
emmeans(prim.mod ~ intervention, type = "response")
```

Longitudinal assessments of the quality of life and impairment are analysed employing Gaussian linear models for repeated measures with intervention group, time, intervention-by-time interaction and study centre as factors and, if the instrument was assessed at baseline, its baseline score as a covariate (mixed model for repeated measurements, MMRM).

The error terms are assumed to follow a multivariate normal distribution with unstructured covariance matrix. Least squares mean changes from baseline will be reported for both groups with 95% CI as well as the difference between the least-squares intervention group means with 95% CI and p-value testing the null hypothesis of no treatment effect ($H_0: \delta = 0$).

```
library(lme4)
library(car)
library(emmeans)

var_sec <- lmer(var ~ baseline_var + intervention + time + intervention * time +
                  site + (1|Patient.Id), data = secEndpoints)
summary(var_sec)
res <- Anova(var_sec, type = "III", test.statistic = "F")
res

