1.2 Objectives and Endpoints

POWER@MS2 investigates the hypothesis that the web- and evidence-based relapse management programme results in more autonomous relapse treatment decision-making by PwMS.

Clinical endpoints are evaluated by the trial statistician, while endpoints related to health economic aspects of the trial are evaluated by the Health Economics team and therefore not specified in this SAP. Primary, secondary and safety endpoints are listed in Table 1.

Table 1 Objectives and related endpoints

	Objective	Endpoint
Primary	To determine whether the programme leads to a decrease in corticosteroid relapse treatment and less intravenous administered corticosteroids in case of steroid treatment.	Proportion of relapses not treated or treated with oral corticosteroids during the follow-up.
Secondary	To determine whether the programme results in more autonomous relapse treatment decisions.	Differences in decision autonomy measured by CPS.
	To determine whether the programme leads to fewer relapses.	Annualised relapse rate.
	To determine whether the programme leads to an increase in risk-knowledge.	Changes in Risk Knowledge.
	To determine whether the programme leads to more empowerment.	Changes in empowerment measured by PAM from baseline to end of study.

	To determine whether the programme leads to a more autonomous steroid treatment decision-making	Changes in PBMS relapses.
Safety	Assessment of safety of the intervention	Changes in HAQUAMS. Changes in HADS. Changes in EDSS. Changes in UNDS.

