2.2 Randomization

PwMS are randomized in a 1:1 allocation ratio to IG or CG stratified by the centre using block randomization through a computer-generated system in secuTrial®.

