2.3 Sample Size

The unit of analysis for the primary endpoint is the occurrence of relapses. Eighty-one relapses per group yield in a power of 85% at two-sided significance level of 5% given proportions of 78% and 56% of orally treated or non-treated relapses in IG and CG. It is expected that this relapse rate can be observed in 170 PwMS with 1 to 2 years follow-up, corresponding to an annual rate of 0.64. The dropout rate is expected to be at 10%. Therefore, 188 PwMS will be randomized.

The blinded sample size recalculation report based on a blinded data export from 10th of September 2021 comprising events of 107 patients at that time with 51 possible and definite relapses ([name], [name] and [name], 2021).

In the first definition of the primary endpoint events, only definite relapses were counted. In the second definition, possible relapses were counted additionally. The first definition resulted in 20 primary endpoint events, while the second resulted in 51 primary endpoint events.

According to the estimated relapse rate per year of 0.8775 (95%-CI: [0.6632, 1.1612]), 125 PwMS need to be followed up for two years. Until 20th of October 2021, 92 patient-years were observed and 58 patient-years documented. With an extension of recruitment for further 3 months and flexible follow-up, the goal of 250 patient-years can be reached. Based on the inclusion of further 39 patients and assuming no change in drop-out rate, 294.3 patient-years can be reached, but only 277 years will be documented as documentation is performed every three months. Therefore, 146 PwMS should be sufficient to reach a power of 85%.

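### The group percentages from the primary-model code are probabilities for a patient with random effect zero, not the proportion of relapses that defines the endpoint

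*SAP*

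**What the plan says.** Table 1 (SAP Section 1.2) defines the primary endpoint as "Proportion of relapses not treated or treated with oral corticosteroids during the follow-up". Section 2.3 works on the same scale. It states that "The unit of analysis for the primary endpoint is the occurrence of relapses", and it derives the sample size "given proportions of 78% and 56% of orally treated or non-treated relapses in IG and CG".

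Section 5.2 analyses the endpoint with a logit mixed model that has a random intercept per patient and fixed effects for group and centre. On the effect measure it says: "The intervention effect is reported as odds ratio (OR) with 95% CI", together with a p-value for OR = 1. The code block ends with the call that begins "emmeans(prim.mod ~ intervention, type = 'response", which requests group means on the response scale. Neither text nor code asks for averaging over the random effect, a bias adjustment, or a difference in proportions.

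If the model fails to converge because the likelihood is flat near zero patient variance, the random effect is dropped, leaving ordinary logistic regression, and GEE is to be explored.

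**The concern.** The logit is non-linear, so the inverse logit of an average linear predictor is not the average probability. In a random-intercept model, back-transforming the fixed part gives the probability for a patient whose random effect is exactly zero. When patients differ in their propensity to avoid intravenous treatment, that is not the share of relapses in the group. By default the centre effects are also averaged on the logit scale before back-transformation, not over the observed centre mix.

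The endpoint is a proportion, and this line is the only place where the plan produces group percentages. Those percentages are therefore likely to be set beside the OR and compared with the observed data and with the planned 78% and 56%. They would match neither, and a reader could not tell why.

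**Working it through.** **Inputs.** From SAP Section 2.3: proportions 0.78 and 0.56, two-sided 5% level, 85% power, 81 relapses per group. From Section 5.2: logit link, normal random patient intercept. Not in the SAP: the between-patient SD on the logit scale, here assumed to lie between 0 and 3.

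**1. The plan's own figure.** Two proportions, pooled variance under the null, no continuity correction, mean proportion (0.78 + 0.56)/2 = 0.67:

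n = [1.960·√(2·0.67·0.33) + 1.036·√(0.78·0.22 + 0.56·0.44)]² / 0.22² = 80.5, so 81 per group.

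Power at 81 is 85.2%. The stated figure is reproduced, which confirms that 78% and 56% were treated as ordinary (marginal) proportions of relapses.

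**2. Marginal effect at the planning values.** Difference 0.78 − 0.56 = 22.0 points. OR = (0.78/0.22)/(0.56/0.44) = 2.79.

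**3. What the code would return.** For each assumed SD s, solve for the group intercept η such that

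∫ expit(η + s·u) φ(u) du = 0.78 (or 0.56),

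using Gauss-Hermite quadrature with 120 nodes. The response-scale group mean is then expit(η), and the patient-specific OR is exp(η_IG − η_CG). Centre effects are left out of this calculation. For example, at s = 1 the solutions are η_IG = 1.510 and η_CG = 0.292, so expit gives 81.9% and 57.2%, and OR = exp(1.510 − 0.292) = 3.38.

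| Assumed SD | IG | CG | Difference (points) | Patient-specific OR |
|---|---|---|---|---|
| 0 | 78.0% | 56.0% | 22.0 | 2.79 |
| 0.5 | 79.1% | 56.4% | 22.8 | 2.94 |
| 1 | 81.9% | 57.2% | 24.7 | 3.38 |
| 1.5 | 85.3% | 58.4% | 26.8 | 4.12 |
| 2 | 88.5% | 59.8% | 28.7 | 5.18 |
| 3 | 93.6% | 62.8% | 30.8 | 8.69 |

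Differences are taken before rounding. The excess over 22 points is 0.8 at SD 0.5, 2.7 at SD 1 and 6.7 at SD 2.

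**4. Is the direction general?** No. With true marginal proportions of 95% and 85% (10 points, OR 3.35) and SD 2, the same calculation gives 98.8% and 94.0%: a gap of 4.8 points, less than half the true one. The patient-specific OR still moves away from 1 (5.32).

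**5. Fallback model.** At SD 0 the two scales coincide (first row). The fallback is triggered only by a variance near zero, so the OR changes little in size there, although its interpretation becomes population-averaged given centre.

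**The case against.** The strongest reply is that the prose commits to the OR and to nothing else. The primary code has no contrast step, whereas the secondary and safety code says explicitly that group differences will be reported. The call is also visibly a sketch, since the comma between model and formula is missing. On this view no percentages and no difference are promised, and an OR for a binary endpoint is ordinary practice.

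Most of this stands. A reader might infer that the plan will publish an inflated risk difference as its headline. The SAP does not say so, and the point differences above are subtractions made for this review. A reader might also infer that the primary test is invalid. It is not, because absence of effect means OR = 1 on both scales. Nor do the documents support a claim that the programme will always look more effective than it is: step 4 shows the opposite at higher rates. Finally, a reader might say that the meaning of the OR turns on convergence. That is so formally, but the fallback applies only where both ORs nearly coincide, so it carries little practical weight.

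The size is open as well. The SAP gives no between-patient variance, and its fallback clause treats a value near zero as possible, in which case the discrepancy is negligible.

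What the reply does not remove is that a pre-specified line of the primary analysis returns group percentages which, whenever the patient variance is positive, do not estimate the endpoint. No other line does.

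**Conclusion.** The point holds as one of reporting and interpretation, not of validity. The conditional OR may remain the primary effect measure, and the sample size of 81 relapses per group reproduces.

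At the planning rates, the displayed gap would exceed the true 22.0 points by nothing at SD 0 and by 6.7 points at SD 2. This rests on a normal random intercept, on true marginal proportions of 78% and 56%, and on assumed SDs. At other observed rates the gap may be too small instead. The change is worth making before the analysis because it concerns the only absolute figures the plan generates for its primary endpoint.

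**What to change.** In SAP Section 5.2:

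- Keep the mixed-model OR, its 95% CI and its test as primary, and add a sentence that this OR is patient-specific.
- Replace the response-scale means line by population-averaged proportions per group. Average the predicted probabilities over the estimated random-effect distribution and the observed centre mix.
- Report their difference with a 95% CI (delta method or a bootstrap that resamples patients) as a supplement to the OR.
- Compute the same marginal proportions in the fallback logistic or GEE branch, so that the percentages mean the same whichever model is used, and say that the OR there is population-averaged given centre.

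The cost is a few lines of code and one or two sentences, with no change to data collection, sample size or the primary test. The line has to be edited anyway to run. The absolute figures may turn out slightly less favourable than those the present line would give.

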# report least square group differences
tmt.means <- emmeans(var_sec, ~ intervention * time)
contrast(tmt.means)
pairs(tmt.means)
```

Safety endpoints that are raised at baseline and at another visit will be analysed using group mean comparisons between the intervention groups (δ) adjusted for baseline assessments and centre in analysis of covariance (ANCOVA) models. Least square group differences will be reported with 95% CIs and p-values testing the null hypothesis of no intervention effect ($H_0: \delta = 0$).

```

library(emmeans)

mod.sec <- lm(var ~ intervention + var_baseline + site,
               data = secEndpoints)

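### Section 5.2 states an unstructured error covariance for the repeated-measures model, but its R code fits a random intercept (compound symmetry), and nothing says which governs

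*SAP*

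**What the plan says.** Section 5.2 of the SAP introduces the model thus: "Longitudinal assessments of the quality of life and impairment are analysed employing Gaussian linear models for repeated measures". The fixed effects are group, time, their interaction, centre and, where available, the baseline score. On the covariance it says: "The error terms are assumed to follow a multivariate normal distribution with unstructured covariance matrix". It promises least-squares mean changes per group and a group difference, with 95% CI and a p-value for a null difference δ.

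The code that follows uses `lmer`, and its formula ends with "site + (1|Patient.Id), data = secEndpoints". No other random term appears. The Type III F-tests and the group-by-time least-squares means are then taken from this fitted object, and `pairs()` is applied to those means.

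A separate paragraph covers ANCOVA: "Safety endpoints that are raised at baseline and at another visit will be analysed using group mean comparisons". In Section 5.1, "United Kingdom Neurological Disability Scale (UNDS) will be used to assess impairment".

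The only non-convergence rule in Section 5.2 belongs to the primary logistic mixed model. Section 5.6 names software only. Neither says whether text or code takes precedence.

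**The concern.** A random intercept with independent residuals of equal variance forces one variance at every visit and one correlation between any two visits. An unstructured matrix leaves every variance and covariance free. An analyst who follows the prose and one who follows the code would fit different models, could report different intervals and p-values, and could each claim to have followed the plan. The choice could also be made after both results are known.

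Where variance changes over follow-up, or correlation weakens as visits lie further apart, the printed code gives wrong standard errors for visit-specific differences and a wrong reference distribution for the interaction test.

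**Working it through.** The plan states no figure on this point, so there is none to reproduce. The check compares the two covariance models and then illustrates the consequence.

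**Inputs from the SAP.** Two-sided 5% level (Section 3.1); the covariance statement and the code (Section 5.2); 146 patients (Section 2.3). Table 2 is damaged as extracted. The UNDS row appears to have nine marks after baseline, one of them possibly the final interview t_x, so k = 8 and k = 9 are both tried.

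**Assumed inputs.** The true covariance. The SD is linear over visits from 1.0 to 1.0, 1.2 or 1.6. For the interaction test, correlation is first-order autoregressive with lag-1 value 0.70, 0.85 or 0.95. Baseline and centre terms are left out.

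**1. Covariance parameters.** The code implies Var(Y) = σ_b²J + σ_e²I, with J the all-ones and I the identity matrix: 2 parameters. Unstructured has k(k+1)/2: 3 for k = 2, 36 for k = 8, 45 for k = 9. The models differ even at two visits.

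**2. Group difference at one visit, complete data, unadjusted.** With a full group-by-time model the point estimates agree. The random-intercept standard error uses the mean variance over visits instead of that visit's variance. With r = visit variance / mean variance, the true type I error is 2Φ(−1.96/√r). For k = 8:

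| SD path | Mean variance | r, last visit | Last visit | r, first visit | First visit |
|---|---|---|---|---|---|
| 1.0 to 1.0 | 1.000 | 1.000 | 5.0% | 1.000 | 5.0% |
| 1.0 to 1.2 | 1.214 | 1.44/1.214 = 1.186 | 2Φ(−1.80) = 7.2% | 1/1.214 = 0.824 | 2Φ(−2.16) = 3.1% |
| 1.0 to 1.6 | 1.729 | 2.56/1.729 = 1.481 | 2Φ(−1.61) = 10.7% | 1/1.729 = 0.579 | 2Φ(−2.58) = 1.0% |

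Nine visits give the same results to within 0.1 points.

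**3. Visit-averaged difference, complete data.** Its model variance is proportional to σ_b² + σ_e²/k. The fit estimates this directly from the between-patient variation of patient means, so the type I error stays at 5.0% on all three SD paths.

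**4. Interaction F-test, complete data, constant SD.** Under the null the numerator and denominator are sums of chi-squares weighted by the eigenvalues of the centred covariance. With k−1 and 144(k−1) degrees of freedom, lag-1 correlations of 0.70, 0.85 and 0.95 give:
- eight visits: 8.6%, 10.0% and 10.9%;
- nine visits: 9.2%, 10.6% and 11.5%.

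Residual degrees of freedom were used, not Kenward-Roger.

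**5. Simulation with the `lmer` random-intercept model.** Eight visits, 146 patients, lag-1 correlation 0.85, complete data, 1500 runs each (Monte Carlo SE 0.6 to 1.0 points):

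| SD path | Last visit | Visit average | Interaction F |
|---|---|---|---|
| Constant | 5.1% | 5.6% | 8.7% |
| 1.0 to 1.2 | 7.0% | 5.5% | 9.1% |

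**6. What `pairs()` prints.** With eight visits there are 16 group-by-visit means and 16 × 15 / 2 = 120 comparisons, Tukey-adjusted, with a critical value of about 3.43. With the SD rising by 20%, the chance that the last-visit group contrast passes that threshold is 2Φ(−3.43/√1.186) ≈ 0.16%, against 0.06% with constant SD. With the SD rising by 60% it is 2Φ(−3.43/√1.481) ≈ 0.48%.

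**The case against.** **The model may govern one outcome, or none.** Section 5.2 names no instrument for it. HAQUAMS, HADS and EDSS each show one later mark in the extracted Table 2, which fits ANCOVA. UNDS is an impairment measure with several later marks, but Table 1 lists it as a safety endpoint and the ANCOVA paragraph could claim it. This stands as a limit on reach. It does not remove the conflict for any outcome that is sent to the repeated-measures model.

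**The larger error rates belong to a test the SAP does not single out.** The prose gives one difference δ and names no last-visit test, and the printed pairwise p-values are Tukey-adjusted. This also stands. If δ is the visit average, complete data leave it at 5%. Of the tests the code prints and that were checked here, the interaction F-test is the one materially affected.

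**The code may be only a template.** It has placeholder variable names, and SAS is allowed instead. That suggests the prose is the specification, but the SAP does not say so.

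**A stronger reading that the documents do not support.** A reader might infer that staggered follow-up pushes the last-visit error to 9% to 15%. Follow-up does vary, between 12 and 36 months, and incomplete late visits can raise this error even with constant SD. But those figures assume that 14% leave before month 24 and the rest end evenly at months 24 to 36, which averages about 27 to 28 months. Section 2.7 states 24 on average, and Section 2.3 gives 294.3 patient-years for 146 patients: 294.3 / 146 × 12 = 24.2 months. The figures are therefore not used here. Nor can the complete-data results be carried over to the multiple imputation planned in Section 5.3, whose effect was not computed.

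**Conclusion.** The text and the code of Section 5.2 specify different covariance models, and the SAP does not reconcile them. That part is certain and does not depend on the damaged table.

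The consequence is conditional. Nothing goes wrong if compound symmetry is true. Otherwise, under the assumed covariances and complete data, unadjusted visit-specific tests range from 1.0% (first visit) to 10.7% (last visit), and the interaction F-test from about 9% to 12%. The visit average holds its level, and the Tukey-adjusted group contrasts at a visit are barely touched.

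It would go too far to conclude that the trial's secondary or safety results as a whole carry inflated error, that UNDS is certainly affected, or that an exact number of covariance parameters is known. The count depends on how t_x is treated, which the SAP does not state.

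This should be corrected before database lock, but it does not threaten the primary analysis.

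**What to change.** Make the code fit the stated model. Options are `mmrm` with `us(time | Patient.Id)`, `nlme::gls` with `corSymm` and `varIdent`, or SAS PROC MIXED with REPEATED TYPE=UN. With it:

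- define how t_x maps to the time levels, with at most one record per patient and level;
- name the simpler covariance to be used on non-convergence, for example heterogeneous first-order autoregressive or Toeplitz, with robust standard errors;
- list the outcomes that this model governs, so that the route for UNDS is explicit.

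If a random intercept is what the authors intend, change the covariance sentence to say so.

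The cost is one code block and a few sentences, with no new data. The drawback is a large number of covariance parameters (36 at eight visits, 45 at nine) with sparse late visits, so the fallback may well be used. The unstructured fit has not been tried on follow-up of this kind, which is a further reason to name the fallback in advance.
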